1.0 Objectives

1.1 Specific aims:

This proposal aims to provide evidence to support use of the NU-FlexSIV Socket for persons with transfemoral (above-the-knee) amputation. This will be accomplished by undertaking a prospective, assessor-blinded randomized cross-over trial comparing comfort and functional performance with the NU-FlexSIV Socket to the standard-of-care ischial containment socket in persons with unilateral transfemoral amputation.

The primary aims of the study are:

Aim 1: To demonstrate if the NU-FlexSIV Socket is more comfortable than the IC socket.

Aim 2: To demonstrate if the NU-FlexSIV Socket results in better functional performance than the IC socket.

Aim 3: To demonstrate the NU-FlexSIV Socket will result in better quality of life and “satisfaction with device” (i.e. prosthesis) than the IC socket.

1.2 Hypotheses to be tested:

Hypothesis 1: We hypothesize that the NU-FlexSIV Socket will provide increased comfort compared to the ischial containment socket.

Hypothesis 2a: We hypothesize that the NU-FlexSIV Socket will allow greater prosthetic side hip range of motion, in particular increased hip extension, leading to increased prosthetic side step length and hence walking speed compared to the ischial containment socket.

Hypothesis 2b: We hypothesize that step width and lateral trunk flexion over the prosthetic limb will not differ between the NU-FlexSIV Socket and ischial containment socket.

Hypothesis 2c: We hypothesize that the NU-FlexSIV Socket will result in faster times to perform the 5-Times Rapid Sit-to-Stand Test, Four Square Step Test and T-Test of Agility compared to the ischial containment socket.

Hypothesis 3: We hypothesize that the NU-FlexSIV Socket will result in better health-related quality of life and satisfaction with device as assessed using the OPUS compared to the ischial containment socket.

2.0 Background

2.1 Relevant prior experience and gaps in current knowledge:

Current prosthetic sockets restrict function, lack comfort and cause secondary health problems. Although designed to support the body and enable effective biomechanical load transfer during walking and other activities, prosthetic sockets interface with residual limb tissues that are neither accustomed nor well-suited to

PROTOCOL TITLE: Functional Performance Evaluation of the Northwestern University Flexible Sub-Ischial Vacuum (NU-FlexSIV) Socket for Persons with Transfemoral Amputation

the high pressure and shear loading that occurs during ambulation with a prosthesis. Despite high daily use (>12 hours), lack of socket comfort is the most common complaint of prosthesis users. Prosthetic sockets lead to many issues due to high pressure, shear stress, temperature and moisture, all of which are exacerbated in highly active persons with amputation and those with irregular residual limbs (e.g. due to traumatic amputation that have irregular shape, extensive scarring, invaginations, skin grafts, painful neuromas, etc.). Residual limb skin problems include cysts, calluses, verrucous hyperplasia, allergic reactions, and bacterial or fungal infections. Residual limb skin problems have been reported by 25% to 63% of persons with amputation in the general population and problems have a negative influence on ability to perform household tasks, prosthesis use, social functioning, and participation in sports.

Sub-ischial sockets challenge conventional understanding of the biomechanics of transfemoral sockets, especially regarding coronal plane stability. In able-bodied walking, the hip abductors, primarily the gluteus medius, maintain pelvic control during single limb stance. Contraction of the hip abductors counters the moment created about the hip by the body center of mass and helps to keep the pelvis level and trunk upright. When the abductors are compromised, lateral trunk lean over the stance limb may be observed (often referred to as a Trendelenberg gait). In the IC socket, skeletal contact over the medial aspect of the ischium and greater trochanter, create a medial-lateral ‘skeletal lock’ for coronal plane control. For sub-ischial sockets, these forces still remain but the socket geometry believed necessary to control them is gone.

The mechanism by which transfemoral prosthetic sockets provide coronal plane stability during gait has been recently debated. Dillon (2007) stated that in an IC socket coronal plane pelvic stability is derived almost entirely from containment of the ischium and ischial ramus and that when containment is not achieved, coronal plane stability is poor. Dillon (2007) has also argued that the ability of any socket to provide coronal plane stability relies in part on the soft tissue, especially the adductors, being compressed to increase stiffness. Compression of soft tissues may occur to a larger extent when vacuum-assisted suspension is used because both the liner and socket are considerably under-sized, potentially contributing to coronal plane stability.

In contrast to existing transfemoral sockets, the NU-FlexSIV Socket does not impinge on the pelvis because it has lower proximal trim lines; is highly flexible allowing muscles to move comfortably within the socket as they contract during activity and improving sitting comfort; and is held securely to the residual limb by suction from a vacuum pump as well as compression from the liner and socket being undersized, making for a firmer connection to the prosthesis.

PROTOCOL TITLE: Functional Performance Evaluation of the Northwestern University Flexible Sub-Ischial Vacuum (NU-FlexSIV) Socket for Persons with Transfemoral Amputation

2.2 Relevant preliminary data:

Our technique requires specific rectifications of the positive model which we have quantified using rectification mapping (Figure 1).

[figure not shown]

Figure 1 Modification pattern averaged across 30 pairs of rectified and unrectified casts of transfemoral residual limbs.

Preliminary tests of individuals using sub-ischial sockets illustrate that they do not use significant trunk lean during walking (Figure 2).

[figure not shown]

Figure 2 Midstance posture of subject wearing a sub-ischial socket (a). Lateral trunk flexion data comparing IC and sub-ischial sockets (b).

PROTOCOL TITLE: Functional Performance Evaluation of the Northwestern University Flexible Sub-Ischial Vacuum (NU-FlexSIV) Socket for Persons with Transfemoral Amputation

To our knowledge, only one other group has demonstrated the efficacy of brimless (i.e., subischial) sockets for persons with transfemoral amputation (Kahle

PROTOCOL TITLE: Functional Performance Evaluation of the Northwestern University Flexible Sub-Ischial Vacuum (NU-FlexSIV) Socket for Persons with Transfemoral Amputation

and Highsmith 2013, Kahle and Highsmith 2014). Using a small (n=10) randomized cross-over trial, gait and balance were found to be equivalent between sockets (IC and brimless) but subjects preferred the brimless socket. In this case, it appears that a rigid IC socket with a flexible brim was cut down to form the brimless socket. Similar improvements in comfort along with better functional outcomes may occur with sockets that are deliberately designed to be subischial, such as the NU-FlexSIV Socket.

3.0 Inclusion and Exclusion Criteria

3.1 Screening for eligibility:

Subjects interested in participating in this study will be screened for eligibility against the inclusion/exclusion criteria by one of the Certified Prosthetists through a clinical exam that assesses the status of the residual limb and walking ability.

3.2 Criteria that define who will be included or excluded in the study:

To participate in the study subjects must:

- be older than 21 years,
- have a unilateral transfemoral amputation,
- have used a prosthesis for two or more years,
- have a residual limb that is stable in volume and free from any wounds,
- be physically fit enough to participate in the performance tests, effectively making them a Medicare Functional Classification Level of K3 (the ability or potential for ambulation with variable cadence - a typical community ambulator with the ability to traverse most environmental barriers and may have vocational, therapeutic, or exercise activity that demands prosthetic use beyond simple locomotion) or K4 (the ability or potential for prosthetic ambulation that exceeds basic ambulation skills, exhibiting high impact, stress, or energy levels - typical of the prosthetic demands of the child, active adult, or athlete),
- have no previous experience of the sub-ischial socket, and
- be expected to be able to complete all visits for the duration of the protocol.

Subjects will be excluded if:

- they have a residual limb femur of less than 5 inches,
- present with any other co-morbidities that affect function, including neurologic abnormalities, e.g. neuropathic pain that would interfere with the study, and/or
- they do not speak and read English.

PROTOCOL TITLE: Functional Performance Evaluation of the Northwestern University Flexible Sub-Ischial Vacuum (NU-FlexSIV) Socket for Persons with Transfemoral Amputation

3.3 Individuals from the following populations will be excluded:

- Adults unable to consent
- Individuals who are not yet adults (infants, children, teenagers)
- Pregnant women
- Prisoners

4.0 Study-Wide Number of Subjects

4.1 Total number of subjects to be accrued across all sites for multi-site trial:

N/A

5.0 Study-Wide Recruitment Methods

5.1 When, where, and how potential subjects will be recruited:

A convenience sample of participants will be recruited primarily by referral of prosthetists in the Chicago-land area. We will recruit both Veteran and non-Veteran subjects to participate in this study. With the assistance of [name], chief of Physical Medicine and Rehabilitation at the Jesse Brown VA Medical Center we will identify and recruit Veterans with unilateral transfemoral amputation. Non-Veteran participants will be recruited from the general community with the assistance of our clinical collaborators at Scheck & Siress Prosthetics, Orthotics and Pedorthics, the largest provider of orthotic and prosthetic clinical care in the Chicagoland area with over 40 certified and licensed orthotic and prosthetic practitioners and twelve accredited facilities.

As a secondary source of recruitment, information about the study will be circulated to other prosthetists in the midwest via the Midwest Chapter of the American Academy of Orthotists and Prosthetists, whose members include prosthetists practicing in Illinois, Indiana and Wisconsin; via amputee support groups and amputee sporting groups in the Chicago land area; as well as via the NUPOC and Scheck & Siress websites and facebook pages.

5.2 Methods to be used to identify potential subjects:

Subjects will be identified primarily by referral from local area prosthetists.

5.3 Materials used to recruit subjects:

Study flyer included in eIRB+ application.

6.0 Multi-Site Research

6.1 Processes to ensure communication among sites for multi-site study:

N/A

6.2 Method for communicating with participating sites:

N/A

PROTOCOL TITLE: Functional Performance Evaluation of the Northwestern University Flexible Sub-Ischial Vacuum (NU-FlexSIV) Socket for Persons with Transfemoral Amputation

7.0 Study Timelines

7.1 Duration of an individual subject's participation in the study, duration anticipated to enroll all study subjects, estimated date for the investigators to complete primary analyses:

- Subjects will participate in this study for approximately 14 weeks (Figure 4).
- It is anticipated that we will recruit 10 subjects per year for each of the first 3 years and 5 subjects in the 4th year of the clinical trial.
- Data will be processed and analyzed for the final subject in month 33

[figure not shown]

Figure 4 Study design and protocol.

of the study.

8.0 Study Endpoints

8.1 Primary and secondary study endpoints:

Our primary end point, socket comfort, will be assessed using the Socket Comfort Score (Hanspal, Fisher et al. 2003) an ordinal scale where 0 = the most uncomfortable socket fit imaginable and 10 = the most comfortable socket fit. Poor socket comfort is one of the most common issues experienced by prosthesis users. Like pain, comfort is subjective and difficult to measure. Therefore, pain-measurement methods such as the numerical rating scale (NRS) were used as models for quantifying and communicating socket comfort. The Socket Comfort Score asks the standard question, “On a 0 to 10 scale, if 0 represents the most uncomfortable socket fit you can imagine, and 10 represents the most comfortable socket fit, how would you score the comfort of the socket fit of your artificial limb at the moment?”

Our secondary end point, functional performance, will be assessed using instrumented motion analysis to record biomechanics of walking at different speeds, a 5-time Rapid Sit-to-Stand Test (RSTS), Four-Square-Step Test (FSST), and T-test of Agility. The 5-time Rapid Sit-to-Stand Test, Four-

PROTOCOL TITLE: Functional Performance Evaluation of the Northwestern University Flexible Sub-Ischial Vacuum (NU-FlexSIV) Socket for Persons with Transfemoral Amputation

Square-Step Test, and T-test of Agility are standardized clinical measures of performance. We will also assess patient reported functional performance, quality of life and satisfaction with device using the Orthotic and Prosthetic Users' Survey (OPUS) (Heinemann, Bode et al. 2003).

8.2 Primary or secondary safety endpoints:

N/A

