All socket fabrication procedures used in this study are consistent with standard clinical care procedures. The standard clinical process of making a transfemoral prosthetic socket involves some loss of modesty and privacy given the intimate fit of the standard-of-care Ischial Containment socket with your groin and buttocks. Certified Prosthetists are trained to ensure privacy during this process. Risk is further minimized by recruiting subjects who have used a prosthesis for at least two years and are therefore familiar with the process.

PROTOCOL TITLE: Functional Performance Evaluation of the Northwestern University Flexible Sub-Ischial Vacuum (NU-FlexSIV) Socket for Persons with Transfemoral Amputation

It is possible that one or both sockets may not be comfortable or that one or both sockets may rub the residual limb and cause redness, blistering, or a sore, just as any new or ill-fitting socket may do. Inclusion/exclusion criteria will help minimize the risk of these problems by only allowing persons to participate who have used a prosthesis for at least two years, have a residual limb that is stable in volume and free from any wounds and no skin/residual limb issues that make fitting a socket problematic. Subjects will actively contribute to minimizing residual limb problems by checking their limb each day, informing investigators of problems as soon as they occur, and working with the study prosthetists to resolve any issues.

Transfemoral amputees are generally at greater risk for stumbling, tripping and falling than people who are not amputees. The risk of stumbling, tripping and falling may be increased while performing some of the mobility tests used in this study. All tests are standardized clinical outcome measures used with amputees and will be performed under controlled lab conditions to ensure that the subject is not distracted from the task and that all other conditions such as ambient lighting, floor surfaces, etc. are favorable, helping minimize risk. Subjects are asked to perform some of the tests “as fast as they can” rather than pushing them to exceed their own comfortable limits, further serving to minimize risk.

(b) Devices used in this research, the purpose of their use, and their regulatory approval status:

Two designs of custom made prosthetic sockets will be compared in this research: (1) the Ischial Containment (IC) Socket and (2) the NU-FlexSIV Socket (Figure 5).

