12.0 Provisions to Monitor the Data to Ensure the Safety of Subjects

N/A

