14.0 Risks to Subjects*

14.1 Foreseeable risks, discomforts, hazards, or inconveniences to the subjects related the subjects' participation in the research:

Participating in this study will expose subjects to many of the same risks as you are regularly exposed to as an above-the-knee prosthesis user.

(1) The standard clinical process of making a transfemoral prosthetic socket involves some loss of modesty and privacy given the intimate

PROTOCOL TITLE: Functional Performance Evaluation of the Northwestern University Flexible Sub-Ischial Vacuum (NU-FlexSIV) Socket for Persons with Transfemoral Amputation

fit of the standard-of-care Ischial Containment socket with the groin and buttocks. This is a temporary situation that occurs primarily during the socket preparation phase of the study.

(2) It is possible that one or both sockets may not be comfortable or that one or both sockets may rub the residual limb and cause redness, blistering, or even a sore, just as any new or ill-fitting socket may do. Regular inspection of the residual limb by the subject at the end of each day will help identify red spots and blisters before they become sores. Immediate communication of these issues to the study investigators and prompt action by the study prosthetist can help minimize the likelihood that red spots become sores.

(3) As transfemoral amputees, all subjects are at greater risk for stumbling, tripping and falling than people who are not amputees. Additionally, the risk of stumbling, tripping and falling may be increased while performing some of the mobility tests used in this study.

14.2 Procedures that may have risks to the subjects that are currently unforeseeable:

N/A

14.3 Procedures that may have risks to an embryo or fetus should the subject be or become pregnant:

N/A

14.4 Risks to others who are not subjects:

N/A

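### Safety endpoints and safety monitoring are entered as N/A, and no collection or analysis of skin problems, falls or reasons for stopping wear is specified by socket

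*Combined protocol and SAP*

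**What the plan says.** Section 8.1 makes socket comfort the primary endpoint and functional performance the secondary one, with OPUS scores alongside. Section 8.2, headed "Primary or secondary safety endpoints", is answered N/A. So is section 12.0, headed "Provisions to Monitor the Data to Ensure the Safety of Subjects".

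Section 14.1 lists three foreseeable risks:
- loss of modesty during fitting;
- the chance that one or both sockets "may rub the residual limb and cause redness, blistering, or even a sore";
- stumbles and falls, with a possible added risk during some of the study's mobility tests.

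Section 2.1 uses skin trouble as part of the case for the trial: "Residual limb skin problems have been reported by 25% to 63% of persons with amputation in the general population". Section 9.3(a) asks subjects to limit harm by inspecting the limb daily, "informing investigators of problems as soon as they occur" and resolving them with the study prosthetists.

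The visit procedures in 9.2 are the Socket Comfort Score, OPUS, gait analysis and three timed tests. Section 9.4 adds patient characteristics and socket measurements. Section 11.1 plans tests of comfort, gait variables, timed tests and OPUS module scores. It also plans a description of missing data and a comparison of participants with and without it. Section 11.4 adds data at week 1 and week 3 and step activity monitors on the test prostheses.

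**The concern.** The first aim-setting sentence of section 1.1 says the trial is to provide evidence for using the new socket. A comfort advantage at week 6 is an incomplete basis for that if nothing is planned to show whether skin breakdown or falls differ between the sockets.

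Equal skin risk cannot be assumed from the design. Section 9.3(b) describes a test socket with a liner one size below the recommendation, a socket 4-6% undersized, and vacuum suspension. The comparator uses skin-fit suction or a locking liner sized as the manufacturer recommends.

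The information will probably reach the team, because subjects must report problems promptly, but the plan gives it no destination. Section 11.3 limits the REDCap entries to what the statistical analysis needs, and no skin or fall analysis exists. Section 11.4 has each socket supplied by a different prosthetist, so unstandardised notes could differ systematically by socket and would be a poor basis for later reconstruction.

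The primary result is also affected. The matched-pairs test needs a value from both periods, and a skin problem is a plausible reason for stopping one socket. Section 11.4 itself expects that some subjects may struggle to keep wearing the less comfortable one.

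**Working it through.** **1. The plan's own figure.** Section 11.2 gives a two-sided matched-pairs t-test, d = 0.754, alpha 0.05, power 0.95, n = 25. Exact noncentral-t power is 0.9425 at n = 24 and 0.9511 at n = 25, so 25 is reproduced. It is sized on comfort alone; the documents give no safety figure. Sections 11.2 and 23.3 enrol 35 and need 25, so the plan tolerates losing 10/35 = 28.6%.

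**2. Named risks against planned data.**
- Skin problems: named in 2.1, 9.3(a) and 14.1; no item in 9.2 or 9.4; no analysis in 11.1.
- Falls: named in 9.3(a) and 14.1; no item in 9.2 or 9.4; no analysis in 11.1.
- Reason for stopping, and the socket worn at the time: early stopping is foreseen in 11.4; no item in 9.4; 11.1 compares those with and without missing data but does not ask why data are missing.

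**3. What a zero count would show.** The one-sided 95% upper bound for zero events among n subjects is 1 − 0.05^(1/n).
- n = 25: 1 − 0.05^(1/25) = 0.113, or 11.3%.
- n = 35: 1 − 0.05^(1/35) = 0.082, or 8.2%.

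**4. Precision of a paired difference.** Assume a proportion p = 0.25 on each socket and within-person correlation ρ. Both are assumptions: 25% is the lower figure in 2.1, which has no time window. Each discordant cell is p(1 − p)(1 − ρ), and the 95% half-width is 1.96 × √(sum of the two cells / n).
- ρ = 0: cells 0.1875 each, sum 0.375. n = 25: 1.96 × √(0.375/25) = 0.240. n = 35: 0.203.
- ρ = 0.3: cells 0.13125 each, sum 0.2625. n = 25: 1.96 × √(0.2625/25) = 0.201. n = 35: 0.170.

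The half-width is therefore about 20 to 24 percentage points at n = 25 and 17 to 20 at n = 35. This is a Wald approximation for planning; an exact interval will differ somewhat.

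**5. Power of a formal test.** Exact McNemar power at two-sided 0.05, for ρ from 0 to 0.3 and assumed rates:
- 25% vs 50%: 0.32 to 0.43 at n = 25; 0.49 to 0.63 at n = 35.
- 10% vs 20%: 0.06 to 0.07 at n = 25; 0.12 to 0.14 at n = 35.

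A powered safety comparison is out of reach at this sample size. Description by socket with intervals is feasible.

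**The case against.** **Recording.** A reader might infer that skin problems and falls will never be recorded. The documents do not show that. Sections 9.3(c) and 9.4 refer to forms filed with the ethics application, which are not in the document, and 11.3 has each prosthetist keep fitting forms that go to the principal investigator. Problems may be noted there. What stands is that no recording or analysis by socket is specified.

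**Dropouts.** A reader might also infer that dropouts could not be interpreted at all. That ignores the missing-data comparison in 11.1 and the week-1 and week-3 data and step monitors in 11.4. These show who stopped and how much they walked. They do not show why, so the narrower point stands.

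**Event rate.** It is tempting to read the 25% to 63% in 2.1 as meaning that events are almost certain in each wear period, so that a simple count would settle the matter. That figure has no time window and describes amputees generally, whereas section 3.2 selects stable, wound-free limbs. At an assumed 5% per 6-week period the chance of at least one affected subject among 25 is 1 − 0.95^25 = 72%; at 2% it is 1 − 0.98^25 = 40%. Seeing an event also says nothing about a difference between sockets.

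**Falls.** Section 14.1 ties fall risk to amputation and to the tests, not to a socket, and stability is compared through the Four Square Step Test, step width and trunk lean. Falls are therefore the weaker half of the case. They are still a named risk without a count.

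**Low risk.** Sections 9.3(b) and 30.2 describe a Class I device, an earlier non-significant-risk finding for the pilot, and close similarity between the sockets. The stated aims make no safety claim. This supports the regulatory position and argues against a formal safety endpoint, but it does not describe harms by socket.

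**Blinding.** Recording the socket worn would unblind the assessor if the assessor did it. This is correct, and the fix has to deal with it.

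**Conclusion.** The point holds as a gap in planned collection and reporting. The two N/A entries are explicit, and they sit beside a risk section that names sores and falls and a procedure that already brings limb problems to the team. Followed as written, the trial could report in favour of the NU-FlexSIV Socket on comfort with no planned account of harms by socket, and with up to 10 of 35 subjects lost for reasons that the plan does not ask for.

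The benefit of closing the gap is descriptive. Zero events would still be compatible with a true rate of up to 11.3% (n = 25) or 8.2% (n = 35). A paired difference would be known only to within about 20 to 24 points at n = 25, assuming 25% on each socket and a within-person correlation of 0 to 0.3. A reader might infer that the trial should be powered to compare safety, or that the new socket is suspected of being less safe. The documents support neither: the sample size cannot carry such a test, and no harm data by socket are given.

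**What to change.** Replace N/A in 8.2 and 12.0, and add to 9.4 a short log of residual-limb skin problems, falls, and reasons for early stopping of wear, each with the socket worn and the period.

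Have it completed at existing visits and problem contacts by the study prosthetists or the gait-lab staff. Both already see the exposed socket, so no extra staff are needed. Keep the log from the blinded assessor.

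In 11.1, plan a descriptive report:
- the number of subjects affected, by socket, among all who wore that socket, so that someone who stops in the first period is still counted;
- the paired difference with an exact confidence interval, among those who wore both;
- reasons for dropout by socket.

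State that this is not a powered safety comparison, and give the bounds and half-widths above with their assumptions.

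The cost is a few form fields, one table and an amendment. No extra visits are needed.
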